3.3. Sample Size Planning

The sample size calculation was based on a two-sided Type I error rate of 5% and a non-inferiority margin of 1.5 mmHg. Assuming a between-treatment difference of 0 mmHg, SD of 4.0 mmHg and a correlation coefficient of 0.6 among repeated measures, approximately 280 adult subjects in total (140 subjects per treatment arm) will provide 70% power to demonstrate non-inferiority of DE-126 Ophthalmic Solution 0.002% to Timolol maleate ophthalmic solution 0.5%. Assuming a drop-out rate of 5%, the final needed sample size will be 294 in total, i.e. 147 subjects/arm.

3.4. Visits and Assessments

There are 5 scheduled visits for each subject. Assessments at each visit and the time/visit window for each post-baseline assessment are specified in the Assessment Schedule (Table 1). For subjects whose study participation is terminated prior to Month 3 (Visit 5, Day 91 ± 3), to the extent possible, all assessments scheduled for Visit 5 will be performed at the early termination (ET) visit. Subjects who have an on-going study medication-related serious adverse event (SAE) at study completion or at ET from the study will be followed by the Clinical Investigator until the event is resolved or determined to be irreversible, chronic, or stable.

Table 1: Schedule of Events and Procedures

	Screening Phase		Double-Masked Treatment Phase				Follow-up Period 2 weeks of post-Last Study Drug Administration ^a
	Visit 1 Screening * Optional Visit 1a	Visit 2 Eligibility / Baseline (Day 1) *	Visit 3 Week 2	Visit 4 Week 6	Visit 5 Month 3 or Early Termination ^a		
Study day	D-28		D1	D14	D42	D90	Study Exit + D14
Visit window in days	+7		NA	±3	±3	±7	+7
Signed and dated informed consent ^b	X						
Inclusion/Exclusion Criteria ^b	X		X				
Demographics and Medical History, including prior PGA ^c	X						
Other prior or Concomitant Medications/Therapies/Procedures	X	X	X	X	X	X	
Dosing Compliance Check				X	X	X	
Adverse Events ^d	X	X	X	X	X	X	X
Pregnancy Test ^e	X		X				
Vital Signs (blood pressure/heart rate) ^f	X		X (08:00)			X (08:00)	
Refraction ^g	X						
BCVA ^g	X	X	X (08:00)	X (08:00)	X (08:00)	X (08:00)	
Slit-lamp Biomicroscopy ^h	X		X (08:00)	X (08:00)	X (08:00)	X (08:00)	
IOP ⁱ	X	X	08:00 10:00 16:00	08:00 10:00 16:00	08:00 10:00 16:00	08:00 10:00 16:00	
Pachymetry ^j	X						
Instill study medication after IOP measurement at site by unmasked site staff and record dosing				X (08:00)	X (08:00)	X (08:00)	
Gonioscopy ^k	X						
Visual Field ^l	X						
Ophthalmoscopy ^m	X		X (16:00)			X (16:00)	
Blood Sampling for PGx ⁿ						X	
Dispense Study Medication & Diary			X		X		
Collect Study Medication & Diary					X	X	
Phone call ^o				X	X	X	X
GQL-15 questionnaire ^p			X			X	

* Visit 1 (Screening) and Visit 2 (Eligibility/Baseline, Day 1) may be combined into one visit for treatment-naïve subjects as long as the additional requirements of Visit 2 (Eligibility/Baseline, Day 1) are fulfilled, and assessment started at 8:00 (±60 min) on the day of the combined visit.

- ^a Optional at unscheduled visit, required for early terminated subjects.
- ^b Informed Consent Form must be signed and dated before study procedures are performed. Informed consent for the optional PGx laboratory research study may be obtained at any visit prior to the study exit.
- ^c Prostaglandin naive subjects are defined as subjects who are not known to have used prostaglandin as their glaucoma treatment. The previous use of prostaglandin should be confirmed by either subject's medical records or subject history.
- ^d AE will be recorded starting after the signing of the informed consent form until 2 weeks post Last Study Drug Administration. Regardless of the source of the reported occurrence of an AE in a subject, the masked investigator will assess the causality of the AE.
- ^e A urine pregnancy test will be conducted for all female subjects of childbearing potential.
- ^f Vital signs (resting blood pressure and pulse rate) will be collected in sitting position anytime at Visit 1 (Screening), and approximately at 08:00 for Visit 2 (Baseline, Day 1), and Visit 5 (Month 3)/exit or early termination before the morning dose.
- ^g Refraction will be performed at the screening visit anytime. If more than 10 letters in BCVA are lost compared to the screening visit, then refraction should be performed again. BCVA examination will be completed before IOP measurement at 08:00.
- ^h Slit-lamp Biomicroscopy examination must be completed before IOP is measured at 08:00. Aqueous flare and cell evaluation will be performed before fluorescein instillation.
- ⁱ IOP measurements using Goldmann applanation tonometer will be performed at 08:00 (± 60 min), 10:00 (± 60 min), and 16:00 (± 60 min) at all visits except for Visit 1 (Screening), and Optional Visit 1a (mid-washout).
- ^j Pachymetry will be performed after IOP measurement at Visit 1 (Screening).
- ^k If gonioscopy was performed within 3 months (90 days) prior to screening and was documented in the subject's records, no additional screening gonioscopy examination is necessary. If needed, Gonioscopy will be performed after IOP measurement at Visit 1 (Screening).
- ^l If visual field test was performed within 3 months (90 days) prior to screening and was documented in the subject's records, no additional screening visual field test is necessary.
- ^m Ophthalmoscopy with pupil dilation will be performed at Visit 1 (Screening) anytime, Visit 2 (Baseline), and Visit 5 (Month 3)/exit or early termination at the 16:00 (± 60 min) after IOP measurements.
- ⁿ Blood sampling for the PGx laboratory research study may be performed at any visit after PGx informed consent obtained, subject randomized, and study drug dosing has begun.
- ^o At Visit 3, 4, and 5, subject will be reminded to take evening dose on the day before each visit. At follow-up Period, subject will be contacted by a phone call to confirm AE after 2 weeks post last study drug administration.
- ^p GQL-15 questionnaire will be administered by subject.

4. DEFINITIONS

4.1. Time-Related Terms

4.1.1. Screening Visit

The *Screening visit* is Visit 1 when subjects will be screened against the inclusion and exclusion criteria. Eligible subjects will be instructed to discontinue use of all IOP-lowering medications, if any, during a washout period.

4.1.2. Baseline Visit

The *Baseline visit* is Visit 2 (Day 1) when the subjects are randomized.

4.1.3. Treatment Start and End Dates, Extent of Exposure (Days)

Treatment start date is the date at which a randomized subject takes the first dose of the study medication. *Treatment end date* is the date at which a randomized subject takes the last dose of the same study medication. For all treatment arms except the placebo arm, if the date of the last dose is missing, then

- The date prior to Month 3 (Visit 5) will be considered the treatment end date for subjects who completed the study, and
- the date prior to ET visit will be used for subjects who prematurely discontinued the study. If the ET visit date of a non-completer is not available, then the date prior to last available visit date will be considered the treatment end date.

The treatment end date will be set to missing if the treatment start date is missing.

The *extent of exposure* to study medication will be assessed by duration of treatment exposure, derived as:

- Duration of treatment exposure = (Treatment end date – Treatment start date) + 1.

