Subjects will be instructed not to show the eye drop bottles or discuss the eye drops to either the Investigator or the Examiner or other study subjects. The active control treatment (Timolol Maleate) bottles will be over-labeled and packaged in the same secondary package (e.g., cardboard carton) as the investigational treatment (DE-126). Subjects in DE-126/Vehicle arm will receive a kit containing 2 bottles labeled "morning" for the morning dose and 2 bottles labeled "evening" for the evening dose. Subjects on Timolol arm will receive a kit containing 2 bottles labeled morning/evening for the BID dosing.

Each eligible subject will receive a numbered study medication kit assigned by Central randomization via Interactive Response Technology (Medidata Rave RTSM) at Visit 2 (Baseline, Day 1) and at Visit 4 (Week 6).

Inclusion Criteria: Please see [Section 5.1 Subject Inclusion Criteria](#)

Exclusion Criteria: Please see [Section 5.2 Subject Exclusion Criteria](#)

Investigational product, dosage, and mode of administration:

Subjects will be randomly assigned in a 1:1 ratio to the DE-126/Vehicle arm and Timolol Maleate arms to receive either DE-126/Vehicle or Timolol Maleate, as described below:

Investigational Product:

DE-126 Ophthalmic Solution contains 0.002% DE-126. Other ingredients include

[REDACTED]

Vehicle:

The vehicle is identical to the investigational product but does not contain the active ingredient DE-126.

Active Control:

Timolol maleate ophthalmic solution 0.5% contains the active ingredient, Timolol 5 mg/ml, and the preservative BAK 0.01%. Other ingredients include monobasic and dibasic sodium phosphate and purified water. The pH is adjusted to 6.5 to 7.5 with sodium hydroxide.

Each subject will be instructed to instill one drop of study medication in each eye at 20:00 and at 08:00 starting the evening of Visit 2 (Baseline, Day 1) through the morning of Visit 5 (Month 3).

Route of Administration of Investigational Product: Topical ocular

Duration of the Study: The study duration includes up to a 5- weeks Screening Period, a 3-month Double-Masked Treatment Period, and up to a 2- weeks Follow-up Period.

Statistical Methods:

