4.4. Schedule of Events and Procedures

The schedule of events and procedures is provided in [Table 3](#).

Table 3: Schedule of Events and Procedures

	Washout Period		Double-Masked Treatment Period				Follow-up Period
	Visit 1 Screening *	Optional Visit 1a	Visit 2 Eligibility/Baseline *	Visit 3 Week 2	Visit 4 Week 6	Visit 5 Month 3 Exit or Early Termination ^a	2 weeks of post-Last Study Drug Administration
Study day	D-28		D1	D14	D42	D90	Study Exit + D14
Visit window in days	+7		NA	±3	±3	±7	+7
Signed and dated informed consent ^b	X						
Inclusion/Exclusion Criteria ^b	X		X				
Demographics and Medical History, including prior PGA ^c	X						
Other prior or Concomitant Medications/ and Therapies/Procedures	X	X	X	X	X	X	
Dosing Compliance Check				X	X	X	
AEs ^d	X	X	X	X	X	X	X
Pregnancy Test ^e	X		X		X	X	
Vital Signs (blood pressure/pulse rate) ^f	X		X (08:00)			X (08:00)	
Refraction ^g	X						
BCVA ^g	X	X	X (08:00)	X (08:00)	X (08:00)	X (08:00)	
Slit-lamp Biomicroscopy ^h	X	X	X (08:00)	X (08:00)	X (08:00)	X (08:00)	
IOP ⁱ	X	X	08:00	08:00	08:00	08:00	
			10:00	10:00	10:00	10:00	
			16:00	16:00	16:00	16:00	
Pachymetry ^j	X						
Instill study medication after IOP measurement at site by unmasked site staff and record dosing				X (08:00)	X (08:00)	X (08:00)	
Gonioscopy ^k	X						
Visual Field ^l	X						

Table 3: Schedule of Events and Procedures (Continued)

	Washout Period		Double-Masked Treatment Period				Follow-up Period 2 weeks of post-Last Study Drug Administration
	Visit 1 Screening	Optional Visit 1a	Visit 2 Eligibility/Baseline	Visit 3 Week 2	Visit 4 Week 6	Visit 5 Month 3 Exit or Early Termination ^a	
Study day	D-28		D1	D14	D42	D90	Study Exit + D14
Visit window in days	+7		NA	±3	±3	±7	+7
Ophthalmoscopy ^m	X		X (16:00)			X (16:00)	
Blood Sampling for PGx ⁿ						X	
Dispense Study Medication & Diary			X		X		
Collect Study Medication & Diary					X	X	
Phone call ^o				X	X	X	X
GQL-15 questionnaire ^p			X			X	

* Visit 1 (Screening) and Visit 2 (Eligibility/Baseline, Day 1) may be combined into one visit for treatment-naïve subjects as long as the additional requirements of Visit 2 (Eligibility/Baseline, Day 1) are fulfilled on the day of this combined visit; in particular, full diurnal IOP measurements (at 08:00, 10:00, 16:00) must be taken.

^a Optional at unscheduled visit, required for early terminated subjects.

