4.3. Safety-Related Definitions

4.3.1. Adverse Event

Events reported on the AE electronic Case Report Form (eCRF) will be assessed according to the recently amended Food and Drug Administration regulations 21 CFR Parts 312 and 320.

Under Protocol 012601IN, an AE is defined as any untoward medical occurrence that occurs in a study subject, regardless of the suspected cause and regardless of timing of study medication administration. An *on-study* AE can occur any time after the date of informed consent through the last study visit. An AE will be considered as *treatment-emergent* if the AE occurred on or after the treatment start date up to the 2 days (twice the scheduled dosing interval) after treatment end date. Treatment-emergent AEs are a subset of on-study AEs. Both on-study and treatment-emergent AEs will be recorded, but only treatment-emergent AEs will be tabulated.

The severity of each AE will be graded by the Clinical Investigator as Mild, Moderate, or Severe.

Each AE will be classified into a system organ class (SOC) and coded to a preferred term (PT) using Medical Dictionary for Regulatory Activities (MedDRA), version 23.1 published in 2020.

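### SAP 4.1.3 dates a missing last dose to the day before the visit, although a subject still on drug is scheduled to be dosed at that visit (minor)

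*SAP*

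**What the plan says.** SAP 4.1.3 defines the treatment end date as the date of the last dose and then gives a fallback, which opens: "For all treatment arms except the placebo arm, if the date of the last dose is missing". The fallback has three branches:

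- Completers: "The date prior to Month 3 (Visit 5) will be considered the treatment end date for subjects who completed the study".
- Non-completers with an ET visit: "the date prior to ET visit will be used for subjects who prematurely discontinued the study".
- Non-completers without an ET date: "then the date prior to last available visit date will be considered the treatment end date".

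If the start date is missing, the end date is left missing. Exposure is then "Duration of treatment exposure = (Treatment end date – Treatment start date) + 1".

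The protocol synopsis has subjects dose both eyes twice daily, "starting the evening of Visit 2 (Baseline, Day 1) through the morning of Visit 5 (Month 3"). Protocol Table 3 carries the row "Instill study medication after IOP measurement at site by unmasked site staff and record dosing", marked at 08:00 for Visit 3, Visit 4 and the combined Visit 5/ET column. The SAP's own schedule (Table 1) has the same row. Protocol 8.1.4 to 8.1.6 place the record in the subject's paper diary.

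The end date also governs the AE tables. SAP 4.3.1 counts an AE as treatment-emergent from the treatment start date "up to the 2 days (twice the scheduled dosing interval) after treatment end date", and tabulates only treatment-emergent AEs. Protocol 8.6.5 defines treatment-emergent by onset or worsening after the first dose and gives no closing date.

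**The concern.** A fallback for a missing last-dose date should give the best available date for the last dose. For a subject still on drug at the visit, the schedule puts a dose on the visit day itself, so the day before is too early by design. The exempted placebo arm does not exist in this two-arm trial, and SAP 4.3.1 cites the protocol number of the earlier placebo-controlled study. The rule was probably carried over from that study, though this is an inference.

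The end date feeds exposure (SAP 7.7) and closes the treatment-emergent window (SAP 4.3.1). It also enters the compliance formula for subjects who withdrew from study medication (SAP 7.6) and the definition of concomitant medication (SAP 4.4.1). A date that is too early understates exposure and removes AEs from the tables. The branch most exposed is the last available visit, because subjects lost to follow-up are plausibly those without a last-dose date. The first diary is collected only at Visit 4, and a subject seen at Visit 4 leaves with a new kit and a new diary.

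**Working it through.** The plan states no figure on this point to reproduce, so the check is date arithmetic on the SAP's own definitions.

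**Inputs.** First dose on the evening of Visit 2, Day 1 (protocol synopsis). Target days 14, 42 and 90 for Visits 3, 4 and 5, with a Visit 5 window of Days 83 to 97 (SAP Table 2). Exposure formula and imputation rule from SAP 4.1.3. Two-day tail from SAP 4.3.1.

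**Step 1: general form.** Let V be the study day of the visit.

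- Rule as written: end = V − 1; exposure = (V − 1) − 1 + 1 = V − 1; window closes on (V − 1) + 2 = V + 1.
- Last dose given on site at the visit: end = V; exposure = V; window closes on V + 2.

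The difference is one day in each. AEs starting on the visit day or the next day stay treatment-emergent because of the tail. Only those starting on V + 2 are lost.

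**Step 2: numbers for a subject whose last dose was the on-site one.**

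| Visit | Day | Exposure, rule | Exposure, dosed at visit | Shortfall | Window closes, rule | Window closes, dosed at visit |
|---|---|---|---|---|---|---|
| 3 | 14 | 13 | 14 | 7.1% | Day 15 | Day 16 |
| 4 | 42 | 41 | 42 | 2.4% | Day 43 | Day 44 |
| 5 | 90 | 89 | 90 | 1.1% | Day 91 | Day 92 |

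At the edges of the Visit 5 window the pairs are 82 vs 83 and 96 vs 97.

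**Step 3: Visit 2 is the last available visit.** The imputed end is the day before the first dose. Exposure = (−1) + 1 = 0 days, and the window closes on Day 2. This arises only if the start date is recorded, because otherwise the end date is left missing.

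**Step 4: subjects lost after Visit 3 or Visit 4.** Assume, as a maximum, that dosing continued to the next scheduled visit.

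- After Visit 3: the window closes on Day 15, so 42 − 15 = 27 on-drug days fall outside it.
- After Visit 4: the window closes on Day 43, so 90 − 43 = 47 on-drug days fall outside it.

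Now remove only the minus-one step and use the visit date as the end. The gaps become 42 − 16 = 26 and 90 − 44 = 46 days. The minus-one step accounts for one day of each gap. The rest comes from closing the window two days after a date inferred from the last visit.

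**Step 5: how many subjects.** The plan allows 5% drop-out: 0.05 × 147 = 7.35, or about 7 per arm. Step 4 concerns only those among them with neither an ET date nor a last-dose date. The documents do not give that share, nor the share of completers with a missing date.

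**The case against.** The strongest reply is that the rule acts only when the last-dose date is missing. If a completer's Visit 5 dose is on record, that is the last-dose date and nothing is imputed. If it is not on record, one cannot say that the imputed date overrides a known dose. This stands in part. The documents place the on-site record in a paper diary and do not say whether it reaches the eCRF field for the last dose. What remains is that, for an on-drug subject, the fallback disagrees with the schedule it is meant to approximate.

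A reader might infer that every imputed date precedes a dose, since every post-baseline visit has one scheduled. The documents do not support that. Protocol 7.1 encourages subjects who have stopped drug to keep attending visits up to Visit 5 on an observational basis, and ET procedures are done only as far as possible. For subjects off drug, the day before the visit may be too late, so the error can run the other way.

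A reader might also infer that the day-before rule itself loses weeks of AEs. Step 4 shows that it does not. The 27 and 47 days also assume continued dosing that nobody can verify, and subjects who cannot be reached report few AEs.

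Finally, on-study AEs are still recorded, and SAP 9.1 lists AEs, AEs leading to death and SAEs separately, so an untabulated event is not hidden. Safety is descriptive, the rule is the same in both arms, and no efficacy conclusion depends on it. All of this stands and keeps the point minor.

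**Conclusion.** The rule is wrong as written for subjects still on drug, and the point is minor. For on-drug completers and ET subjects with a missing date, it costs one day of exposure and the AEs that start exactly two days after the visit. Where Visit 2 is the last visit, it gives a dosed subject an end date before the first dose and zero exposure, which no reading of the definition can justify. For subjects lost after Visit 3 or Visit 4, up to 27 or 47 on-drug days could go untabulated, though any AEs reported would still be listed. Those figures are maxima that rest on dosing to the next scheduled visit, and they come almost entirely from closing the window on an imputed last-visit date. The number of subjects is unknown; for the lost-subject branch it is some part of the planned 5% drop-out. The conclusion does not extend to subjects who stopped drug and attend observationally.

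**What to change.** In SAP 4.1.3:

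1. Delete the opening clause that exempts a placebo arm.
2. Use the latest documented dose date, from the on-site record or the diary, as the floor for the imputed end date. That is the visit date itself when a dose was given at the visit.
3. State that the end date can never precede the treatment start date.

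In SAP 4.3.1, for subjects lost to follow-up whose end date is imputed, do not close the treatment-emergent window on that date. Count AEs through last contact, in line with Protocol 8.6.5, which sets no closing date.

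The cost is a few lines of SAP text and one derivation change, made before unmasking. It needs the on-site and diary dose dates to be available to the programmers, which should be confirmed. The downside is that a few late AEs in lost subjects may be counted as treatment-emergent after dosing had in fact stopped.

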4.1.4. Study Day

The *study day* describes the relative day of an observation starting with the reference date designated as Study Day 1.

In this study, for efficacy analyses, the randomization date is the reference day and the study day will be calculated as:

- For days prior to the randomization date, Study Day = Date – Randomization Date.
- For days on/after the randomization date, Study Day = Date – Randomization Date + 1.

For safety analyses, the treatment start date is the reference day and the study day will be calculated as:

- For days prior to the treatment start date, Study Day = Date – Treatment Start Date.
- For days on/after the treatment start date, Study Day = Date – Treatment Start Date + 1.

Note that there is no Study Day 0.

4.1.5. Days on Study

The *days on study* measures the duration of stay since randomization in the study. For each randomized subject, the days on study will be derived as:

$$\text{Days on Study} = (\text{Study Exit date} - \text{Baseline Visit Date}) + 1.$$

4.1.6. Analysis Visit Window and Out-of-Window Measurements

For this study, a measurement collected at a visit is an *out-of-window* measurement if the study day of the visit falls outside of a visit window specified in Assessment Schedule (Table 1Table 1), or a *within-window* measurement otherwise.

Analysis visit is a timing variable to be used for analyses involving visits. For each analysis visit, an *analysis window* is set up to determine the analysis visit a measurement should be mapped to. The analysis visit of a measurement will be determined based on the study day of the measurement and specified analysis windows and is not necessarily the same with the study visit where the measurement was collected. For example, an out-of-window measurement collected at the Week 2 study visit will be mapped to the Week 6 analysis visit, if the study day of the measurement falls into the analysis window of Week 6.

The following *analysis windows* for post-baseline visits will be applied to minimize the amount of missing data for analysis purposes:

Table 2: Post-Baseline Analysis Visit and Analysis Window

Post-Baseline Analysis Visit (Target Assessment Date)	Protocol Visit Window	Analysis Window
Week 2 (Day 14)	[11, 17]	[2-25]
Week 6 (Day 42)	[39, 45]	[26-61]
Month 3 (Day 90)	[83, 97]	[62-

For analyses involving post-baseline visits, if there are two or more measurements that fall into the same analysis window of a post-baseline visit, then a visit in which IOP are measured at all the scheduled timepoints (8:00, 10:00 and 16:00) will be selected for that analysis visit. In case that there are two or more such visits within the same analysis window, the measurement closest to the target assessment day will be selected for that analysis visit. In the case that two measurements are closest and equidistant to the target assessment day, i.e., one is before, and one is after the target assessment day, the later one will be selected for that visit.

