- **If the study drug administration is discontinued prior to Visit 5, then to the extent possible, all procedures for Study Exit/Early Termination as per Table 3 will be performed on the day of early termination. Subjects who are discontinued from the study early will not be replaced.**
- **If subject requires an unscheduled visit, procedures and assessments will be performed as needed.**

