9.2. Best-Corrected Visual Acuity

BCVA measures the acuteness or clearness of the best-corrected vision, with a range of [0, 97] in ETDRS letters. An increase in BCVA indicates an improvement in the best-corrected vision.

BCVA will be measured for each eye prior to the 08:00 IOP measurement at each visit at Baseline, Week 2, Week 6, and Month 3 using a Snellen chart using visual acuity chart (Early Treatment Diabetic Retinopathy Study [ETDRS] chart) and the logMAR scoring.

BCVA in Snellen scale will be converted to logMAR scale using the following equation and be used in all the BCVA analyses:

$$\text{LogMAR VA} = -\log_{10} \left(\frac{\text{Snellen numerator}}{\text{Snellen denominator}} \right)$$

BCVA (logMAR scores) and changes from baseline will be summarized by treatment and analysis visit for study eyes and fellow eyes, separately. In addition, any change (worsening or improvement) of ≥ 0.2 LogMAR (2 lines) from baseline will be summarized and listed.

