9.3. Slit-lamp Biomicroscopy

For each biomicroscopy parameter, frequency and percentage of severity rating score will be summarized by actual treatment received and analysis visit for study eyes and fellow eyes, separately. In addition, subjects with improvement (decrease) or worsening (increase) or maintaining from baseline in severity rating score will be tabulated by analysis visit and biomicroscopy parameter. Subjects with worsening of 2 units or more from baseline will be listed.

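### The one-visit-per-window rule in SAP 4.1.6 leaves some unscheduled and early-termination exams out of the by-visit safety tables, and a 1-unit slit-lamp worsening at such an exam reaches no planned slit-lamp table or threshold listing

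*SAP*

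**What the plan says.** The rule in SAP 4.1.6 opens without any limit to efficacy: "For analyses involving post-baseline visits, if there are two or more measurements that fall into the same analysis window of a post-baseline visit". The first criterion for choosing among them is then completeness of the pressure readings: "then a visit in which IOP are measured at all the scheduled timepoints (8:00, 10:00 and 16:00) will be selected for that analysis visit". If more than one visit qualifies, "the measurement closest to the target assessment day will be selected for that analysis visit", and a tie goes to the later one. SAP Table 2 sets contiguous windows: Days 2–25 (Week 2), Days 26–61 (Week 6) and Day 62 onward (Month 3).

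The rule belongs to the time-related definitions of SAP 4.1, which also serve safety. SAP 4.1.4 states: "For safety analyses, the treatment start date is the reference day". SAP 9.2 provides that "BCVA (logMAR scores) and changes from baseline will be summarized by treatment and analysis visit". SAP 9.3 provides that "subjects with improvement (decrease) or worsening (increase) or maintaining from baseline in severity rating score will be tabulated by analysis visit and biomicroscopy parameter". The SAP gives no other selection rule for safety measures.

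Two outputs stand beside the by-visit tables. SAP 9.2 summarizes and lists BCVA changes of 0.2 logMAR or more. For the slit lamp, SAP 9.3 adds: "Subjects with worsening of 2 units or more from baseline will be listed". Neither says whether exams that lost the selection count.

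On extra visits, Protocol 8.1.6 says: "If subject requires an unscheduled visit, procedures and assessments will be performed as needed". Note a to Protocol Table 3 makes the Visit 5 assessments, which include three IOP times, required at early termination and optional at unscheduled visits. Protocol 7.1 encourages subjects who stop study drug to attend the remaining visits for observation.

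**The concern.** Whether IOP was read at three clock times has no bearing on the validity of a slit-lamp grade or an acuity score. Yet as written, that criterion, followed by distance from the target day, decides which eye exam enters the safety tables. Exams outside the schedule are the ones that lose.

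Protocol 2.3 names conjunctival hyperemia as the most common reaction to DE-126 and advises caution with intraocular inflammation. If a graded worsening is seen at an unscheduled or early-termination exam and has gone by the selected visit, the by-visit tables show no worsening. At stake is whether the descriptive graded-worsening rates by arm are complete.

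**Working it through.** **Inputs.** Target days, protocol windows and analysis windows: SAP Table 2. Visit tolerances: SAP Table 1. Selection order: SAP 4.1.6. Drop-out of 5% and 294 subjects: SAP 3.3. The first dose is due on the evening of Day 1 (Protocol 4.1), so the efficacy and safety study days normally coincide.

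**Step 1: the plan's own figures.** 14 ± 3 = [11, 17]; 42 ± 3 = [39, 45]; 90 ± 7 = [83, 97]. All three match SAP Table 2.

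**Step 2: candidate days.** Reference case: scheduled visits on Days 14, 42 and 90 with complete IOP. An extra exam can fall on Days 2–89, which is 88 days, less Days 14 and 42: 86 days. The windows are contiguous, so each of these days belongs to one.

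**Step 3: unscheduled exam, all scheduled visits attended.**
- Without full diurnal IOP, it loses on completeness on 86 of 86 days. This stays at 100% for every combination of in-window visit days tried: all days for Weeks 2 and 6, and Month 3 on Day 83, 90 or 97.
- With full IOP, it loses on distance on 86 of 86 days in the reference case. Over the same combinations the range is 73–100%. The low end has visits on Days 11, 39 and 97. The extra exam then wins on Days 12–17, 40–45 and 84–96 (6 + 6 + 13 = 25 of 93 days), so 68/93 = 73% are lost.

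**Step 4: early-termination exam, subject exits.**
- Lost to Week 2: Days 15–25 = 11 days. Lost to Week 6: Days 43–61 = 19 days. Total 30; 30/86 = 35%.
- Kept, as the only visit in its window: Days 2–13 (12), 26–41 (16) and 62–89 (28). Total 56; 30 + 56 = 86.
- Range with full IOP: 24/93 = 26% to 30/79 = 38%. Without full IOP: 26% to 36/79 = 46%.

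**Step 5: early-termination exam, subject continues observational visits.** Each window then also holds a scheduled visit, so Step 3 applies and 73–100% of days are lost. For example, an exam on Day 70 is 20 days from target and loses to a Day 90 exam done about 20 days after drug was stopped.

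**Step 6: number of exams.** 5% of 294 = 14.7, about 15 subjects. If all exit and their exits are spread evenly over days (an assumption): 15 × 0.26 = 3.9 and 15 × 0.46 = 6.8, so about 4 to 7 exit exams. The reference case gives 15 × 0.35 = 5.2. The number of unscheduled exams cannot be estimated from the documents.

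**Step 7: which clause does the work.** Remove the IOP-completeness preference and keep closest-to-target. In the reference case the losses do not change: 30 of 86 days if the subject exits, 86 of 86 if visits continue. The ranges become 26–38% and 73–100%.

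**Step 8: where a change at a non-selected exam could still appear.**

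| Change | By-visit table | Threshold output | AE tables |
|---|---|---|---|
| BCVA, 0.2 logMAR or more | no | summary and listing; use of all exams not stated | if reported as an AE |
| Slit lamp, 2 units or more | no | listing; use of all exams not stated | if reported as an AE |
| Slit lamp, 1 unit | no | none | if reported as an AE |

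Anterior chamber cells rising from grade 0 to grade 1 (6–15 cells, SAP Table 4) is a 1-unit change and falls in the last row.

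**The case against.** The strongest reply is that one record per window, chosen by distance from the target, is ordinary practice, and that harm has its own route. Protocol 8.6.1.1 and Appendix D make a significant change in condition, or a clinically significant abnormal assessment, an adverse event. SAP 9.1 tabulates ocular events by arm, relationship and maximum severity, none of which depends on SAP 4.1.6. Early-termination procedures are due, where possible, on the day drug is stopped, which is within the treatment-emergent period of SAP 4.3.1. A painful eye or iritis that prompted a visit should therefore be counted there.

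This stands, and it narrows the point. It does not close it, because adverse-event reporting rests on judged significance and does not replace the graded exam data.

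The reply is also right that the IOP-completeness clause is not the sole cause. Early-termination visits require three IOP times, so they usually lose on distance. Limiting that clause alone would recover little (Step 7).

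It could be said that the clause was meant for IOP only. The text does not say so, and closest-to-target would still drop most of these exams.

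**Conclusion.** The point holds for the by-visit BCVA and slit-lamp tables. The clear gap is a 1-unit slit-lamp worsening at a non-selected exam, so graded worsening rates in these descriptive tables may be understated. The loss is 35% of possible days for early-termination exams when the subject exits (range 26–46%), and 73–100% when visits continue. The count of 4 to 7 exams rests on the planned drop-out and evenly spread exits. A share of days is not a share of subjects.

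The documents do not support four stronger readings:

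- **Vision loss at such exams goes unreported.** SAP 9.2 summarizes and lists changes of 0.2 logMAR or more with no visit limit. It needs clarifying, but the output exists.
- **The safety comparison with timolol is biased towards no difference.** Only descriptive by-visit tables are affected, the number of extra visits per arm is unknown, and SAP 6 plans no safety testing.
- **Extra exams are mostly prompted by eye problems.** This is plausible, but the documents do not state it.
- **40% of early-termination days are lost.** Counting only Days 15–89 gives 30/75 = 40%, but that leaves out Days 2–13, when the exam is kept.

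**What to change.** 1. Keep the by-visit tables. Add to SAP 9.3 a by-arm summary of maximum post-baseline worsening for each slit-lamp parameter over all scheduled, unscheduled and early-termination exams. Count any increase in anterior chamber cells and flare. This is the change that matters, since no post-baseline exam is dropped.
2. State in SAP 9.2 that the 0.2 logMAR summary and listing use all post-baseline exams, and in SAP 9.3 that the 2-unit listing does too.
3. Limit the IOP-completeness criterion in SAP 4.1.6 to IOP endpoints.

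The cost is SAP wording and one extra table from data already collected. Worst-value rates will be somewhat higher than by-visit rates in both arms, and the table should be labelled so that the two are not compared directly.
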